## 11. Adverse Events: Assessing and Reporting Requirements

An AE is defined as any untoward medical occurrence in a subject or clinical investigation subject administered a pharmaceutical product, and which does not necessarily have to have a causal relationship with the treatment. An AE can therefore be any unfavorable and unintended sign (including an abnormal laboratory finding, for example), symptom, or disease temporally associated with the use of a medicinal product or protocol-specified procedure, whether or not considered related to the medicinal product or protocol-specified procedure. Any worsening (i.e., any clinically significant adverse change in frequency and/or intensity) of a preexisting condition that is temporally associated with the use of the study product is also an AE.

All AEs that occur on study, within 30 days of the last administration of the study treatment, must be reported. The reporting timeframe for AEs meeting the criteria of SAE is described in Section 11.

AEs are reported in a routine manner during the study using the EDC system. Additionally, certain AEs must be reported in an expedited manner for timelier monitoring of subject safety and care. The following list of AEs (Sections 11.1, 11.4, and 11.6) and the characteristics of an observed AE will determine whether the event requires expedited reporting to the Sponsor or designee.

Electronic monitoring of AEs will be done through the EDC system and/or via email reporting by each clinical site to the Sponsor and/or Sponsor's safety designee. Per GCP, all sites must enter data in a timely manner. AEs meeting the criteria of SAE in the EDC system will trigger immediate review and distribution as needed and required by regulatory authorities.

The investigator or qualified designee will assess each subject to evaluate for potential new or worsening AEs at the time points specified in the protocol and more frequently if clinically indicated.

### 11.1. Adverse Events and Potential Risks List

For a list of the adverse events and potential risks associated with NT-I7, please refer to the most recent version of the Investigator's Brochure.

### 11.2. Adverse Event Characteristics

**CTCAE term (AE description) and grade:** The descriptions and grading scales found in the CTCAE version 5.0 will be utilized for AE reporting. All appropriate treatment areas should have access to a copy of the CTCAE version 5.0. A copy of the CTCAE version 5.0 can be downloaded from the Cancer Therapy Evaluation Program (CTEP) website [http://ctep.cancer.gov/protocolDevelopment/electronic\\_applications/ctc.htm](http://ctep.cancer.gov/protocolDevelopment/electronic_applications/ctc.htm).

#### For expedited reporting purposes only:

- AEs of Special Interest for the protocol are outlined in Sections 11.4 and 11.6.

#### Attribution of the AE:

- Definite – The AE is *clearly related* to the study treatment.

- Probable – The AE is *likely related* to the study treatment.
- Possible – The AE *may be related* to the study treatment.
- Unlikely – The AE is *doubtfully related* to the study treatment.
- Unrelated – The AE is *clearly NOT related* to the study treatment.

### 11.3. Expedited Adverse Event Reporting

AE, SAEs, and other reportable safety events will be reported by the subject (or, when appropriate, by a caregiver, surrogate, or the subject's legally authorized representative).

The investigator, who is a qualified physician, and any designees are responsible for detecting, assessing, documenting, and reporting events that meet the definition of an AE or SAE as well as other reportable safety events. Investigators remain responsible for following up of AE, SAEs and other reportable safety events for outcome.

Expedited AE, including AESI, reporting for this study must be done by notifying the Sponsor and/or Sponsor's safety designee **within 24 hours** of the investigator or investigator designee knowledge of the event *via* the study EDC system and email ([contact] and [contact]) as stipulated.

In the rare occurrence when Internet connectivity is lost, a 24-hour notification is to be made to the Sponsor designated CRO, ICON Safety Helpline, by telephone at [contact], fax ICON Safety Fax Line, [contact] or [contact]. Once Internet connectivity is restored, the 24-hour notification phoned in must be entered electronically into the data capture system by the original submitter at the site.

#### 11.3.1. Time Period and Frequency for Collecting AE, SAE and Other Reportable Safety Event Information

- All AEs, SAEs and other reportable safety events that occur after the consent form is signed but before treatment /allocation must be reported by the investigator, if the event causes the subject to be excluded from the study or is the result of a protocol-specified intervention, including but not limited to washout or discontinuation of usual therapy, diet, or a procedure.
- All AEs from the time of treatment/allocation through 30 days following cessation of study treatment or starting of new anticancer therapy, whichever is earlier, must be reported by the investigator.
- All AEs meeting serious criteria, from the time of treatment/ allocation through 90 days following cessation of study treatment or initiation of new anticancer therapy, whichever is earlier, must be reported by the investigator.
- All pregnancies and exposure during breastfeeding, from the time of treatment/ allocation through 90 days following cessation of study treatment or initiation of new anticancer therapy, whichever is earlier, must be reported by the investigator.
- Additionally, any SAE brought to the attention of an investigator at any time outside of the time period specified above must be reported immediately to the Sponsor if the event is considered to be drug-related.

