Prior medications – Record all medications (prescription and over-the-counter [OTC]) taken within 30 days of Screening visit. Concomitant medications – Enter all medications (prescription and OTC) taken between 7 days prior to Cycle 1, Day 1 through the Safety Follow-up visit.

Full physical exam is required during Screening, Day 1 of every cycle, End of Treatment, and Safety Follow-up visits. A directed physical exam may be performed on other days as clinically indicated.

Performance status must be assessed per ECOG Performance Scale criteria.

Vitals (blood pressure, heart rate, respiratory rate, temperature) to be collected in a standardized manner in a sitting position after the subject has rested comfortably for ~5 minutes. On the odd-numbered cycles (pembrolizumab and NT-I7), vitals need to be obtained within 60 minutes prior to the start of the pembrolizumab infusion AND repeated after the completion of the pembrolizumab infusion, but before the NT-I7 injection. On the even-numbered cycles (pembrolizumab only), vitals need to be obtained within 60 minutes prior to the start of the pembrolizumab infusion.

Height is measured on the first visit during Screening only.

All AEs, including those meeting serious criteria, from the time of consent through the 30-day safety follow-up visit, and AEs meeting serious criteria only from 30 days following cessation of study treatment to 90-day safety follow-up visit. See Section 11 for additional details on reporting of AEs.

Duplicate EKG, at least 5 minutes apart, and serum cardiac enzyme levels (Troponin (TnI or TnT) and CK-MB) must be obtained at Screening, C1D1, every 4 cycles (i.e., C5D1, C9D1,..), and End of Treatment. A patient should be assessed by a PI or a local cardiologist to determine if the EKG and the serum cardiac enzyme levels are clinically significant. If either is found to be clinically significant, see footnote 30.

Hematology includes complete blood count (CBC) with differential, including but not limited to red blood cell (RBC) count, hemoglobin, hematocrit, white blood cell (WBC) count with differential (neutrophil count including lymphocyte, monocyte, eosinophil, basophil counts and bands), absolute neutrophil count (ANC), and platelet count.

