## 8.2. Dose Modification of Pembrolizumab

The toxicity of pembrolizumab could be accentuated by administration of NT-I7 and the component attributable to pembrolizumab and NT-I7 will be difficult if not impossible to sort out. Thus, the management of pembrolizumab will be used for the treatment of any AE. NT-I7 treatment will be discontinued when pembrolizumab must be **permanently discontinued**.

AEs associated with pembrolizumab exposure may represent an immune-related response. These irAEs may occur shortly after the first dose or several months after the last dose of pembrolizumab treatment and may affect more than one body system simultaneously. Therefore, early recognition and initiation of treatment is critical to reduce complications. Based on existing clinical study data, most irAEs were reversible and could be managed with interruptions of pembrolizumab, administration of corticosteroids and/or other supportive care. For suspected irAEs, ensure adequate evaluation to confirm etiology or exclude other causes. Dose modification and toxicity management guidelines for irAEs associated with pembrolizumab are provided in [Table 4](#).

When study interventions are administered in combination, attribution of an adverse event to a single component is likely to be difficult. Therefore, while the investigator may attribute a toxicity event to the combination, to NT-I7 alone, or to pembrolizumab alone, for adverse events listed in [Table 4](#), both interventions must be held according to the criteria in .

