## 9.2. Medications Used with Caution

No data exist regarding the interaction of NT-I7 with drugs known to prolong the QT/QTc interval. Accordingly, subjects receiving these drugs while receiving NT-I7/pembrolizumab therapy should be closely monitored.

No data exist regarding the interaction of NT-I7 with commonly used vitamins, minerals, supplements, herbal and natural remedies. Accordingly, these drugs should be avoided, or used with caution at the investigator's discretion, and closely monitored while the subject is receiving the study treatment.

All treatments that the investigator considers necessary for a subject's welfare may be administered at the discretion of the investigator in keeping with the community standards of medical care. For example, subjects can continue using medically prescribed marijuana/ Marinol for purposes such as cancer related fatigue, nausea, vomiting, appetite improvement etc. while participating in the study.

*All concomitant medications will be recorded on the eCRF including all prescription, over-the-counter (OTC) products, herbal supplements, and IV medications and fluids. If changes occur during the study period, documentation of drug dosage, frequency, route, and date should also be included on the eCRF.*

All concomitant medications received within 7 days prior to the first dose of study treatment and up to 30 days after the last dose of study treatment should be recorded. Concomitant medications administered 30 days after the last dose of study treatment should be recorded for SAEs and events of special interest or clinical interest (ECIs) as defined in Sections **11.4** and **11.6**.

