### 11.4. Adverse Events of Special Interest in NT-I7

The following AEs are of special interest in subjects receiving NT-I7, as defined below and must be reported by the investigator expeditiously to the Sponsor and/or Sponsor's Safety designee irrespective of regulatory seriousness criteria and the relatedness to NT-I7.

Immune-related adverse event (irAE) is defined as an AE associated with drug exposure that is consistent with an immune-mediated mechanism of action when there is no clear alternate etiology. For events which are potentially immune-related, additional information such as serologic, immunologic, and histologic (biopsy) data and use of steroids or immunosuppressants will be used to support an irAE diagnosis.

- Potential drug-induced liver injury that includes an elevated ALT or AST  $\geq 3 \times$  ULN in combination with an elevated bilirubin  $\geq 2 \times$  ULN and, at the same time, an alkaline phosphatase (ALP)  $< 2 \times$  ULN; no other reason can be found to explain the combination of increased AST or ALT, and TBL, such as viral hepatitis A, B, or C; preexisting or acute liver disease; or another drug capable of causing the observed injury. (86)
- Conditions (regardless of grade) suggestive of an autoimmune disorder or immune-related adverse events (irAEs), including but not limited to hepatitis, pneumonitis, colitis, pancreatitis, endocrinopathies (including but not limited to thyroiditis, Type 1 diabetes mellitus, adrenal insufficiency), myocarditis, myositis/polymyositis, rheumatoid arthritis, vasculitis, neuritis, systemic lupus erythematosus, Sjogren's syndrome, multiple sclerosis, Guillain-Barre syndrome and myasthenia gravis
- Symptoms and signs suggestive of hypersensitivity, cytokine release, or infusion reaction syndromes with a different underlying pharmacological etiology
- Grade  $\geq 2$  diarrhea
- Grade  $\geq 2$  AST/ALT and Grade  $\geq 2$  total bilirubin elevation with constitutional symptoms
- Grade  $\geq 3$  hypoxia or dyspnea
- Grade  $\geq 2$  pleural effusion that is not due to the underlying disease (e.g., non-malignant pleural effusion)

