4.11.2 Adverse Events

AE will be coded using MedDRA version 27.1 and graded using the NCI-CTCAE version 5.0.

A TEAE is any AE that starts on/after the first day of study treatment or that worsens on/after the first day of study treatment, and up to 30 days (90 days for serious adverse events [SAEs]) after the date of last dose of study drugs, or initiation of new anticancer therapy, whichever is earlier.

For the purpose for regulatory reporting, relationships of “definite”, “probable” and “possible” to study drug as assessed by the investigator will be defined as related to study treatment. Missing relationship will not be imputed.

Adverse events of special interest (AESIs) in NT-I7 are defined in protocol section 11.4. Events of clinical interest (ECI) in pembrolizumab are defined in protocol section 11.6.

An overall summary of TEAEs using frequencies and percentages of subjects will be presented based on the following categories:

- TEAEs
- NT-I7-related TEAE
- Pembrolizumab-related TEAE
- Either NT-I7 or pembrolizumab-related TEAE
- TEAEs with Grade 3 or higher
- NT-I7-related TEAE with Grade 3 or higher
- Pembrolizumab-related TEAE with Grade 3 or higher
- Either NT-I7 or pembrolizumab-related TEAE with Grade 3 or higher
- Serious TEAE
- NT-I7-related serious TEAE
- Pembrolizumab-related serious TEAE
- Either NT-I7 or pembrolizumab-related serious TEAE
- TEAEs leading to NT-I7 interrupted/held
- TEAEs leading to NT-I7 dose reduced
- TEAEs leading to NT-I7 permanently withdrawn
- TEAEs leading to pembrolizumab interrupted/held
- TEAEs leading to pembrolizumab permanently withdrawn
- TEAEs leading to discontinuation from the study
- AESI in NT-I7
- ECI in pembrolizumab
- TEAEs considered injection site reaction (ISR)
- TEAEs considered infusion-related reactions (IRR)
- TEAEs leading to death

The above events will be tabulated by SOC and PT. SOC will be sorted by descending frequency and then alphabetically for ties. Within each SOC, PT will also be sorted by descending frequency and then alphabetically for ties, by the overall number of subjects in Phase 1b/Phase 2a total. If a PT is reported more than once for a subject, the subject will only be counted once in the incidence for that PT.

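### Non-serious AESIs starting 31 to 90 days after the last dose have no clear collection rule and fall outside the SAP's AESI tables

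*Protocol*

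**What the plan says.** **What must be reported.** Protocol Section 11.4 requires expedited reporting of NT-I7 AESIs "irrespective of regulatory seriousness criteria and the relatedness to NT-I7". The list opens to low-grade events through "Conditions (regardless of grade) suggestive of an autoimmune disorder or immune-related adverse events (irAEs", followed by examples such as pneumonitis, thyroiditis and myocarditis. No end date is given.

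**When events are collected.** Section 11.3.1 asks for "All AEs from the time of treatment/allocation through 30 days following cessation of study treatment", or up to new anticancer therapy if that comes first. Its next item extends the period to 90 days for serious events only, with the same cut-off at new therapy. Beyond that, only drug-related SAEs are reportable. The opening of Section 11 repeats the 30-day limit. Footnote 9 to the Schedule of Assessments (Section 7.4) asks for "AEs meeting serious criteria only from 30 days following cessation of study treatment to 90-day safety follow-up visit".

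**What is expected after day 30.** Section 9.2 says that concomitant medications given after day 30 "should be recorded for SAEs and events of special interest or clinical interest (ECIs", and points to Sections 11.4 and 11.6 for the definitions. Section 8.2 states that "irAEs may occur shortly after the first dose or several months after the last dose of pembrolizumab treatment".

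**How events are analysed.** SAP 4.11.2 counts an event as treatment-emergent if it starts or worsens on treatment or "up to 30 days (90 days for serious adverse events [SAEs]) after the date of last dose of study drugs", or until new anticancer therapy if that is earlier. AESIs are one category of the overall treatment-emergent summary, which is then tabulated by system organ class and preferred term. They take their definition from protocol Section 11.4 and have no window of their own.

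**The concern.** Sections 11.4 and 9.2 treat AESIs as a class that matters regardless of seriousness and that can arise after day 30. Sections 11 and 11.3.1 and footnote 9 divide the follow-up by seriousness alone. A site that sees a new non-serious immune-related event on, say, day 45 can find support in the protocol both for reporting it and for not doing so. Capture would then vary by site.

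The SAP adds a second filter. Even where a site follows Section 11.4 and enters the event, the event is not treatment-emergent and so does not reach the AESI incidence tables. What is at stake is the reported frequency of late immune-related events for a T-cell-expanding agent added to a checkpoint inhibitor. Section 8.2 itself describes late onset of such events.

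**Working it through.** There is no stated figure to reproduce. The check is a comparison of rules, some day counting, and the direction of the effect.

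**1. One case against every rule.** Take a non-serious thyroiditis with onset on day 45 after the last dose, with no new anticancer therapy started.

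| Rule | Day-45 non-serious AESI |
|---|---|
| Protocol 11.4 | Reportable; no end date |
| Protocol 11.3 and 11.3.3 | AESIs go by the 24-hour route, and expedited events must also be in routine data |
| Protocol 9.2 | Related concomitant medications to be recorded |
| Protocol 11 (opening) | Outside the 30-day period |
| Protocol 11.3.1 | Not required: past day 30 and not serious |
| Protocol 7.4, footnote 9 | Not required: serious only |
| SAP 4.11.2, treatment-emergent definition | Not treatment-emergent |
| SAP 4.11.2, AESI row and tables | Excluded, as part of the treatment-emergent summary |
| SAP 5, interim AESI table | Excluded; the table is labelled as treatment-emergent |
| SAP 4.11.2, listings of all AEs and of AESIs | Shown, if entered |

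Three protocol rules point to capture and three do not. The SAP lists the event but does not count it.

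**2. Length of the gap.** The follow-up for serious events is 90 days and for non-serious events 30 days. The gap is 90 − 30 = 60 days, and 60/90 = 67% of the follow-up days. It is shorter for a subject who starts new anticancer therapy between days 30 and 90, and absent for one who starts it by day 30, because both windows then close.

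**3. Comparison with the SAP's own exposure period.** SAP 4.8 computes NT-I7 duration as (last dose − first dose + 43)/7 weeks. Inclusive counting accounts for +1, so 43 − 1 = 42 days after the last NT-I7 dose count as exposure. If NT-I7 was given at the last dosing visit, days 31-42 (42 − 30 = 12 days) are exposure time in which a new non-serious event is not treatment-emergent. If the last cycle was pembrolizumab only, the window reaches about 21 + 30 = 51 days after the last NT-I7 dose and this mismatch disappears.

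**4. Direction.** Let N be the treated subjects in an arm, a those with a tabulated AESI, and b those whose only AESI is non-serious with onset on days 31-90. The tables report a/N; the incidence to day 90 is (a + b)/N. The difference is b/N, which cannot be negative. The documents give no rate for late-onset events, so b is unknown. As a scale only, one such subject moves the rate by 1/30 = 3.3 percentage points in a Phase 2a arm of 30 and by 1/10 = 10 points in a Biomarker Cohort of 10.

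**The case against.** The strongest reply is that Section 11.4 is a specific duty that sits beside the general rule in 11.3.1. It has no end date, AESIs follow the 24-hour route, and Section 11.3.3 requires expedited events in the routine data as well. On that reading late AESIs do reach the database, and the SAP lists them. This stands in part. A reader might infer that these events are lost, but the documents do not bar them. They leave collection ambiguous and exclude the events from the incidence tables. The reply does not remove the ambiguity, because footnote 9 says serious only, and a listing does not correct an incidence table.

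The 30/90-day split is also deliberate: the log for version 7.0 records the revision of footnote 9. An irAE judged to be an important medical event is serious and is collected to day 90. Both points are correct. They narrow the gap to ordinary non-serious events but do not reconcile footnote 9 with Sections 11.4 and 9.2.

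A reader might also infer that the AESI rate is the main tolerability measure. Neither document says so. The named safety endpoints are adverse events overall and DLTs in Phase 1b, which is complete, and adverse events in the Biomarker Cohort. AESIs are one safety category among several.

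Finally, the AESI row in SAP 4.11.2 does not itself carry the treatment-emergent label. It does sit under the treatment-emergent summary, and the corresponding interim table in SAP Section 5 carries the label, so exclusion is the natural reading.

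**Conclusion.** The inconsistency is real and worth correcting. For non-serious AESIs with onset on days 31-90 and before new anticancer therapy, the protocol gives sites conflicting instructions, and the SAP leaves such events out of the AESI tables even when they are entered. Reported AESI incidence to day 90 can only be understated, and only for the late-onset events that Section 8.2 describes.

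The size in events cannot be computed. It is tempting to turn 60 of 90 days into a loss of two thirds of the post-treatment non-serious AESIs. That would need uniform onset over the 90 days and no subject starting new therapy, and the documents support neither assumption. Events during up to 35 cycles of treatment and the following 30 days are unaffected, so the effect on the overall AESI rate may be small.

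The conclusion rests on reading the AESI row as part of the treatment-emergent summary.

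**What to change.** **Protocol.** Reconcile Section 11.3.1, the opening of Section 11 and footnote 9 with Sections 11.4 and 9.2. State once that AESIs as defined in Section 11.4 are collected regardless of seriousness through the 90-day Safety Follow-up visit or the start of new anticancer therapy, whichever is earlier. The 30-day wording in the expedited-reporting heading of Section 11.3.2 should be aligned at the same time.

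**SAP.** In 4.11.2, apply the 90-day limit to AESIs as well as SAEs for the AESI tables, and use the same rule for the interim AESI table in Section 5. The listings need no change. The SAP change is useful by itself, because late AESIs already entered under Section 11.4 would then be counted.

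**Cost.** A sentence in each place. The 90-day clinic visit and its adverse event review already exist. There will be a few more non-serious records and a slightly higher AESI rate. Subjects already past follow-up, including those in the completed Arms IV and V, may have incomplete late AESI data. The CSR should say so, particularly wherever Arm IV is set beside IVa or Arm V beside Va. A 90-day limit will still miss events with later onset.
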